### **5.3 Impact COVID-19 on study visits**

A listing of visits impacted by COVID-19 will be presented for all participants based on the ES. This will include visit, visit date, relative day, impact category, relationship to COVID-19 and the narrative of the event. The number and percentage of participants with visits impacted by COVID-19 will be summarized for treatment group for relationship to COVID-19 and impact category by country. The denominator for the percentages will be the number of participants in the ES.

## **6 DEMOGRAPHICS AND OTHER BASELINE CHARACTERISTICS**

### **6.1 Demographics**

Baseline demographic variables will be summarized by treatment group and overall using the FAS.

The following continuous variables will be summarized using descriptive statistics:

- Age (years), as recorded in the electronic Case Report Form (eCRF) (will not be derived)
- Height (m)
- Weight at screening (kg) (at Screening and at Admission [Day -1])
- Body Mass Index (BMI) (kg/m^2)

The BMI value collected in the eCRF will not be used for this summary. The BMI will be recalculated using the following formula and reported to 1 decimal place:

$$BMI \text{ (kg/m}^2\text{)} = \frac{Weight \text{ (kg)}}{(Height \text{ (m)})^2} \quad [3]$$

The following categorical variables will be summarized using frequency counts and percentages:

- For the EudraCT reporting, the age categories will include:
  - 18 - < 65 years
  - 65 - ≤ 85 years
  - ≥ 85 years
- For the clinicaltrials.gov reporting, the age categories will include:
  - ≤18 years
  - 19 to <65 years
  - ≥65 years
- Sex

- Race
- Ethnicity

By-participant listings of demographic data will be provided by treatment group using the ES. This will include year of birth, age (years), sex, race and ethnicity, height (m), weight at screening (kg), weight at admission (kg), and BMI (kg/m^2).

By-participant listings of childbearing potential information will be provided by treatment group using the ES.

## **6.2 Other Baseline characteristics**

Lifestyle will be summarized by treatment group and overall using the FAS. The following categorical variables will be summarized using frequency counts and percentages:

- Alcohol use (Never, Current, Former)
- Caffeinated beverages use (Never, Current, Former)
- Tobacco use (Never, Current, Former).

By-participant listings of lifestyle data will be provided by treatment group for the ES. In addition to the items presented above, the listing will include stop date of tobacco use (or ongoing, as applicable) and illicit drug use.

## **6.3 Medical history and concomitant diseases**

Previous and ongoing medical history conditions will be summarized by treatment group and overall using the FAS. The summary will include the following:

- Number and percentage of participants with any previous and ongoing medical history conditions.
- Number and percentage of participants with previous and ongoing medical history conditions by MedDRA system organ class (SOC) and preferred term (PT).

By-participant listings of previous and ongoing medical history conditions will be provided by treatment group for the FAS. This will include MedDRA SOC and PT, reported condition, start date and stop date (or status ongoing, as applicable).

By-participant listings of procedure history and concomitant medical procedures will be provided, by treatment group for the ES. This will include reported procedure term and procedure date.

## **6.4 Prior and concomitant medications**

### **6.4.1 Definitions of prior and concomitant medications**

If a participant takes a medication before the date of study medication administration, this medication will be categorized as 'prior medication'. With this definition, any medication recorded that has been taken for at least 1 day before the date of study medication administration will be considered as prior. This includes medications that started prior to study medication administration and continued after.

Medication not stopped before the date of study medication administration will be classified as ‘concomitant medication’. Medication will also be labeled as ‘concomitant medication’ when the start date is between the date (including the date) of study medication administration and the date of the participant’s last study visit.

From the definitions above, any medication that started prior to dosing and continued after dosing will be classified as both prior and concomitant.

Any medications with missing dates and/or times will be handled as described in [Section 4.2.4](#) in order to classify them as prior or concomitant.

#### **6.4.2 Presentation of prior and concomitant medications data**

Prior and concomitant medications will be summarized by treatment group and overall using the FAS. The summary will include the following:

- Number and percentage of participants with any prior medications.
- Number and percentage of participants with prior medications by ATC class, presenting WHO-DD Anatomical Main Group (ATC Level 1), Pharmacological Subgroup (ATC Level 3), and preferred term.
- Number and percentage of participants with any concomitant medications.
- Number and percentage of participants with concomitant medications by ATC class, presenting WHO-DD Anatomical Main Group (ATC Level 1), Pharmacological Subgroup (ATC Level 3), and preferred term.

By-participant listings of prior and concomitant medications will be provided by treatment group for the FAS. This will include Anatomical Main Group, Pharmacological subgroup, preferred term, reported term, dose per intake and unit, frequency, formulation, route, indication, category (prior/concomitant/prior and concomitant), start date and end date (or ongoing, as applicable).

### **7 MEASUREMENTS OF TREATMENT COMPLIANCE**

As this is a single dose study and dosing is performed in-house by the investigator or member of staff, no specific assessment or compliance is warranted. Any dosing deviation will be addressed in the DEM and described in the CSR.

### **8 EFFICACY ANALYSES**

Efficacy is not evaluated in this study.

### **9 PHARMACOKINETICS AND PHARMACODYNAMICS**

#### **9.1 Pharmacokinetics**

Unless otherwise specified, all analysis described in this section will be performed on the PK-PPS.

##### **9.1.1 Descriptive analysis of Pharmacokinetics data**

Individual plasma concentrations of bimekizumab will be listed by treatment group for the FAS and will include the actual and nominal sampling times and the corresponding time deviations. The window allowance document will define the acceptable deviations at each timepoint;

samples obtained outside this tolerance will be considered as protocol deviations. All protocol deviations will be discussed at the DEM and any exclusion from analysis will be documented accordingly ([Section 3.4](#)).

Plasma concentrations of bimekizumab will be summarized by treatment group and nominal sampling time. This will include number of participants, arithmetic mean, median, SD, minimum, maximum, geometric mean and geometric CV and 95% CI for the geometric mean (assuming log-normally distributed data).

Individual plasma concentration-time profiles of bimekizumab will be displayed graphically on linear and semi-logarithmic scale. In addition, combined individual (spaghetti) plots will be displayed by treatment group with all participants in a given treatment group overlaid on the same plot (linear and semi-logarithmic scale).

Geometric mean profiles with lower and upper limits of the 95% CI for the linear scale and without confidence limits for the semilogarithmic scale will be displayed. The mean plots will be displayed on the same graph.

All figures will include a reference line for the LLOQ on the semi-logarithmic panel.

The following PK parameters (see definitions in [Section 2.2.1](#)) will be derived from the plasma concentrations of bimekizumab:

- Primary PK parameters
  - AUC, AUC(0-t), Cmax
- Secondary PK parameters
  - t1/2, tmax
- Other/Exploratory PK parameters
  - %AUCex
  - CL/F
  - Vz/F

For calculation of the PK variables, the actual sampling times will be used.

All PK variables will be listed and summarized by treatment group for the PK-PPS including number of participants, arithmetic mean, median, SD, minimum, maximum, geometric mean, geoCV and 95% CI for the geometric mean.

The following rules will apply for the PK data summaries:

- Values below the LLOQ will be reported as BLQ for individual data and will be substituted with LLOQ/2 for the descriptive statistics
- Descriptive statistics of PK concentrations will be calculated only if at least  $\frac{2}{3}$  of the individual data at a specific sampling timepoint are measured and are quantifiable (i.e., above LLOQ) and if  $n \geq 4$ . If  $n < 3$ , then only n, minimum and maximum will be presented and if  $n = 3$ , then only n, median, minimum and maximum will be presented and the other descriptive statistics will be left blank

- Descriptive statistics of PK parameters will be calculated only if at least  $\frac{2}{3}$  of the individual data are calculable and if  $n \geq 4$ . If  $n < 3$ , then only  $n$ , minimum and maximum will be presented and if  $n = 3$ , then only  $n$ , median, minimum and maximum will be presented and the other descriptive statistics will be left blank. For  $t_{max}$ , only  $n$ , median, minimum and maximum will be presented
- If no participant has data, only  $n=0$  will be presented
- The 95% lower and upper CI should be left blank if the SD (or equivalently the geoCV) is equal to 0
- The geoCV will be calculated using the following formula where SD is the standard deviation of the log-transformed values:

$$\text{Geometric CV (\%)} = \sqrt{(\exp(SD^2) - 1)} \times 100 \quad [3]$$

## 9.2 Statistical analysis of bioequivalence

### 9.2.1 Primary analysis

The primary PK parameters (AUC,  $AUC_{(0-t)}$  and  $C_{max}$ ) will be evaluated according to a univariate model of analysis of variance (ANOVA). The model will include treatment group as a fixed effect. The dependent variables will be logarithmically transformed by natural logarithms ( $\ln$ ) prior to analysis.

Two independent comparisons will be made:

- Test 1: Bimekizumab-SS-2mL versus Reference 1: Bimekizumab-SS-2x1mL
- Test 2: Bimekizumab-AI-2mL versus Reference 2: Bimekizumab-AI-2x1mL

For each comparison, the difference between the least squares means (LSM) will be estimated and back transformed in order to obtain the geometric mean ratio for the corresponding Test/Reference together with the 90% CI for the ratio.

For each of the respective comparisons, BE will be concluded if the 90% CIs for the ratio of the respective comparison are fully included in the acceptance range from 0.8 to 1.25 for AUC,  $AUC_{(0-t)}$  and  $C_{max}$ .

All participants in the PK-PPS will be included in the analysis as far as the data permit; a participant may be included in the analysis for one or more PK variables (i.e., if it was not possible to calculate AUC for a given participant, the participant may be included in the analysis of BE for  $AUC_{(0-t)}$  and  $C_{max}$ ).

The results of the BE analysis will be tabulated, for each comparison, including the geometric least squares means and 90% CI for treatment group, the estimated geometric mean ratio and 90% CI for the corresponding Test/Reference as well as the CV%.

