##### **Weight**

4. Body weight minimum of 50kg for male and 45kg for female study participants and a maximum of 100kg for all study participants, and BMI within the range 18 to  $32\text{kg/m}^2$  (inclusive) at the Screening Visit.

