## 2.4 Determination of sample size

This is a formal BE study to compare the PK of bimekizumab-SS-2mL (test 1) versus bimekizumab-SS-2x1mL (reference 1), and bimekizumab-AI-2mL (test 2) versus bimekizumab-

---

AI-2x1mL (reference 2). Two independent comparisons will be made (i.e., test 1 versus reference 1 and test 2 versus reference 2).

The between subject variability (CV%) observed in previous small studies following a single dose administration of bimekizumab in healthy study participants (i.e., UP0031, RA0124, UP0033, and UP0074) was 21% to 25% for AUC and 23% to 33% for Cmax.

Assuming a geometric mean ratio of 0.9 between each pair of formulations and a between subject variability (CV%) of 33%, 93 study participants per group are required to assess BE (using an acceptance range of 0.8 to 1.25) with 80% power at the 5% significance level. If the true mean ratio between each pair of formulations is 0.95, then with the same assumptions on variability and significance level there is >95% power to determine BE for that pair of formulations.

Sample size estimation was performed using SAS software (version 9.4).

Assuming a dropout rate and non-evaluable study participants of approximately 10%, 100 study participants per group for a total of 400 study participants are to be enrolled in the study. If this 10% rate is likely to be exceeded, due to unforeseen circumstances during the COVID-19 pandemic, then participants may be replaced.

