**Table 3-1: Expected Baseline Visits**

Measurement	Definition of Baseline
Vital signs	Day 1, Pre-dose value or, if missing, Day -1 value or, if both are missing, the screening value.
Body weight	Day -1 value or, if missing, the screening value.
Single 12-lead ECG	Day 1, Pre-dose value or, if missing, Day -1 value or, if both are missing, the screening value.
Hematology (including coagulation/hemostasis)	Day -1 value or, if missing, the screening value.
Clinical Chemistry	Day -1 value or, if missing, the screening value.
Urinalysis	Day -1 value or, if missing, the screening value.
ADAb status	Day 1 Pre-dose value

ADAb=anti-drug antibody; ECG=electrocardiogram

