### **3.8 Changes to protocol-defined analyses**

None.

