## **4 STATISTICAL/ANALYTICAL ISSUES**

### **4.1 Adjustments for covariates**

There are no planned analyses including adjustments for covariates.

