#### **4.2.1 Pharmacokinetic concentration data**

Measurements that are BLQ will be imputed with half of the LLOQ for the purpose of calculating the geoMean and its 95% CI, the geoCV, the arithmetic mean, and SD for summaries and figures. If any summary value (geoMean, arithmetic mean, lower CI level or minimum) is lower than LLOQ, then 'BLQ' will be displayed.

For the individual figures, any concentrations that are BLQ will be regarded as missing, with the exception of pre-dose measurements BLQ on Day 1, which will be imputed with zero for linear scale plots.

Additional rules for PK data summaries are provided in [Section 9.1.1](#).

Pharmacokinetic concentration data will not be available to the study team until after the last scheduled procedure for the last study participant in the study, so the decision to replace participants who dropped out or are missing PK visits due to COVID-19 can be made in an unbiased manner.

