### 9.2.3 Sensitivity analysis

The following sensitivity analyses will be performed following the same model as described for the primary analysis (Section 9.2.1):

1. Based on all nonpositive ADAb participants (Defined as any positive ADAb observed post baseline)
2. Including body weight at Day -1 as covariate
3. Corrected for measured protein content:

For compliance with Canadian Health ministry guidance, AUC and  $C_{max}$  ratio estimates and 90% CIs will be also presented as corrected for measured protein content (potency). A correction factor (CF) will be obtained as the ln-transformed ratio of the percent protein content (Reference/Test). Then, this factor will be added to the difference in LSMS to obtain, by exponentiation, the corrected AUC and  $C_{max}$  geometric mean ratios and its 90 % CIs.

For a given Reference/Test, the correction factor will be calculated using the below formula:

$$CF = 100 \times \exp\left(\frac{\% \text{ Measured Content Reference}}{\% \text{ Measured Content Test}}\right) \quad [4]$$

The corrected ratio estimate for the PK parameter (AUC or  $C_{max}$ ) is calculated using the below formula:

$$Ratio = 100 \times \exp(LSM \text{ difference} + CF) \quad [5]$$

Where,

$$LSM \text{ difference} = LSM(\text{Test}) - LSM(\text{Reference}) \quad [6]$$

The corrected 90% CI for the ratio is obtained using the below formula:

$$90\% \text{ CI} = 100 \times \exp[(LSM \text{ difference} + CF) \pm t_{0.05,n} \times se(LSM \text{ difference})] \quad [7]$$

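### The primary BE model is valid but leaves Day -1 body weight, already collected and already modelled, to a sensitivity analysis, and SAP 4.1 wrongly says no covariate-adjusted analysis is planned

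*SAP*

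**What the plan says.** SAP 9.2.1 analyses ln(AUC), ln(AUC(0-t)) and ln(Cmax) by ANOVA and states: "The model will include treatment group as a fixed effect". Protocol 9.4.1 specifies the same model. Bioequivalence is concluded for a device pair if the 90% CIs for all three parameters lie within 0.8 to 1.25.

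On covariates the SAP says two different things:

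- Section 4.1: "There are no planned analyses including adjustments for covariates".
- Section 9.2.3, item 2 of the sensitivity analyses that are to be performed with the primary model: "Including body weight at Day -1 as covariate".

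Everyone receives a fixed 320 mg dose. Eligibility allows a wide weight range: "Body weight minimum of 50kg for male and 45kg for female study participants and a maximum of 100kg for all study participants". Protocol 6.3 describes 1:1:1:1 randomization and no stratification. SAP Table 3-1 defines baseline body weight as "Day -1 value or, if missing, the screening value". SAP 2.4 gives the sample size: "93 study participants per group are required to assess BE".

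**The concern.** In a parallel-group study the CI width is driven by between-subject variability. With a fixed dose and roughly a two-fold permitted weight range (45 or 50 kg to 100 kg), part of that variability may be due to weight. The treatment-only model leaves all of it in the residual error. The sponsor thought weight relevant enough to model, yet kept it out of the analysis that decides bioequivalence.

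What is at stake is the chance of showing bioequivalence when it is true. The enrolment target leaves slightly fewer evaluable participants than the plan requires, so there is no spare precision at the planning assumptions. A chance imbalance in weight between arms is not the issue. It is sampling error that the unadjusted CI already covers.

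The conflict between SAP 4.1 and 9.2.3 is a separate matter. As worded, one section denies that the other's analysis is planned, so the status of the weight-adjusted result is open to argument when it is reported.

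**Working it through.** **Inputs from SAP 2.4 and 9.2.1:** ratio (GMR) 0.9; CV 33%; limits 0.8 to 1.25; 90% CI, that is two one-sided 5% tests; 93 per group for 80% power; 100 per group enrolled with about 10% loss. Observed CVs were 21% to 25% for AUC and 23% to 33% for Cmax.

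**Input not in the documents:** R², the share of ln(PK) variance explained by weight. It is shown below as a range.

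**Method.** SD on the log scale = √ln(1 + 0.33²) = 0.3215. Power is the exact two one-sided tests power, integrated over the variance estimate. With weight in the model the SD is multiplied by √(1 − R²). Degrees of freedom are 2n − 2 unadjusted and 2n − 3 adjusted.

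**1. Reproducing the plan.** At n = 93, power is 80.1% at GMR 0.9 and 97.7% at GMR 0.95. This agrees with the stated 80% and >95%. Pooling the error over four arms also gives 93.

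**2. Validity.** At a true ratio of 0.80 the unadjusted test has an exact type I error of 5.0%. Simulation with R² = 0.20 gave 4.7% for the ANOVA and 4.9% for the weight-adjusted model.

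**3. Evaluable numbers.** 100 × (1 − 0.10) = 90 per group, below 93. Replacement is foreseen only if the 10% rate is likely to be exceeded.

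**4. Effect of adjustment at n = 90, CV 33%, GMR 0.9.**

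| R² | CI half-width factor √(1 − R²) | Power |
|---|---|---|
| 0 (unadjusted) | 1.000 | 78.9% |
| 0.05 | 0.975 | 80.7% |
| 0.10 | 0.949 | 82.5% |
| 0.20 | 0.894 | 86.3% |
| 0.30 | 0.837 | 90.0% |

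Power reaches 80% at R² = 0.031. If weight explains nothing, almost nothing is lost: simulated power at n = 93 was 80.1% unadjusted and 80.0% adjusted.

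**5. Plausible R².** Assume exposure varies as weight to the power −b, with b from 0.5 to 1, and an SD of ln(weight) of 0.13 to 0.17. Neither figure is in the documents. Then R² = (b × SD of ln weight / SD of ln PK)².

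| Parameter (SD of ln PK) | b = 0.5 | b = 0.75 to 1 |
|---|---|---|
| Cmax, CV 33% (0.3215) | 4% to 7% | 9% to 28% |
| AUC, CV 25% (0.2462) | 7% to 12% | 16% to 48% |

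For example, the lowest Cmax value is (0.5 × 0.13 / 0.3215)² = 0.041 and the highest is (1 × 0.17 / 0.3215)² = 0.280.

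**6. Milder planning values, n = 90, unadjusted.** Power is 97.3% at GMR 0.95 with CV 33%. At GMR 0.9 it is 88.9% with CV 28% and 94.0% with CV 25%. In the last case R² = 0.20 raises it to 97.3%, about 3 points.

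**7. Size of a chance imbalance.** A one-standard-error weight difference between arms moves the ratio by exp(b × SD of ln weight × √(2/90)) − 1. That is 1.0% to 1.3% for b = 0.5 and 1.5% to 2.6% for b = 0.75 to 1. The standard error of the ln ratio is 0.3215 × √(2/90) = 0.048, so the shift is well inside the existing uncertainty.

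**8. The text conflict.** Section 4.1 is not limited to the primary analysis. Section 9.2.3 lists the weight-adjusted model among analyses that will be done. Both statements cannot be true as written.

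**The case against.** The strongest reply is that nothing here is an error. The unadjusted ANOVA is valid, matches protocol 9.4.1 and rests on the same unadjusted CV as the sample size. The weight-adjusted ratio will be reported anyway, so the dispute is only about which prespecified analysis decides. That is right about validity, but the choice still sets the width of the deciding CI.

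The 78.9% comes from enrolment: 93/0.9 gives 104 per group, not 100. With 93 or more evaluable, power is at least 80% without adjustment. This also stands. The shortfall shows why precision matters but does not cause the loss of it.

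The size of the gain is assumed. At the weakest exponent considered (R² 4% to 7%) Cmax power is about 80.4% to 81.4%, only 1.5 to 2.5 points above 78.9%. The gain matters mainly for Cmax at the top of its CV range and at GMR 0.9, while AUC, where weight may explain more, already has ample power. All these powers are for a single parameter. Joint power for the three was not computed.

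Protocol 4.2 says the design follows a bioequivalence guideline and scientific advice, neither of which is available here. An adjusted primary model might not fit them. This is the main reason for caution.

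Finally, 4.1 may have been meant for the primary analysis only. It does not say so.

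**Conclusion.** The concern holds as a recommended improvement, with medium confidence. The primary analysis is valid, but it gives up precision that a pre-dose, already collected covariate could provide for one degree of freedom. At 90 per group, CV 33% and GMR 0.9, the gain in single-parameter power runs from about 2 points at R² = 0.05 to 11 points at R² = 0.30, and the CI half-width falls by about 3% to 16%. The size depends wholly on the assumed R². An R² of about 3% is enough to bring power back to 80%. At milder ratios or CVs the gain is small.

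The contradiction between SAP 4.1 and 9.2.3 needs no assumption and should be corrected whatever is decided about the model.

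**What to change.** 1. Prespecify ln(Day -1 body weight), with the screening value if Day -1 is missing, as a covariate in the primary model for AUC, AUC(0-t) and Cmax. This also settles the scale of the covariate, which 9.2.3 leaves open.
2. Keep the treatment-only ANOVA as the sensitivity analysis.
3. Make the change before exposure data are seen. The SAP already provides the window: "Pharmacokinetic concentration data will not be available to the study team until after the last scheduled procedure for the last study participant".
4. Amend protocol 9.4.1 and SAP 9.2.1, and record the departure in SAP 3.8 ("Changes to protocol-defined analyses"), which now reads none.
5. In either case, reword SAP 4.1 to name the weight-adjusted analysis in 9.2.3.

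**Cost.** No new data and one degree of freedom. Items 1 to 4 need a protocol and SAP amendment, and the sponsor should first confirm that a covariate-adjusted primary analysis fits the guideline and scientific advice behind the design. Item 5 alone is a one-line correction.

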## **9.4 Planned outcome analyses**

### **9.4.1 Analysis of the primary endpoints**

The PK analyses will be performed on the PK-PPS.

The primary PK parameters ( $C_{max}$ ,  $AUC_{(0-t)}$ , and  $AUC$ ) will be evaluated according to a univariate model of analysis of variance (ANOVA). The model will include treatment group as a fixed effect. The dependent variables will be logarithmically transformed prior to statistical testing, following the usual recommendations. Natural logarithms (ln) will be employed. The 90% confidence interval (CI) of the adjusted geometric mean ratios will be calculated. Two independent comparisons will be made (ie, test 1 versus reference 1 and test 2 versus reference 2). For each of the respective comparisons, BE will be concluded if the 90% CIs for the ratio of the respective comparison are fully included in the acceptance range from 0.8 to 1.25 for  $AUC$ ,  $AUC_{(0-t)}$ , and  $C_{max}$ .

Sensitivity analyses may also be performed on the PK parameters.

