## **9.9 Determination of sample size**

This is a formal BE study to compare the PK of bimekizumab-SS-2mL (test 1) versus bimekizumab-SS-2x1mL (reference 1), and bimekizumab-AI-2mL (test 2) versus bimekizumab-AI-2x1mL (reference 2). Two independent comparisons will be made (ie, test 1 versus reference 1 and test 2 versus reference 2).

The between subject variability (CV%) observed in previous small studies following a single-dose administration of bimekizumab in healthy study participants (ie, UP0031, RA0124, UP0033, and UP0074) was 21% to 25% for AUC and 23% to 33% for  $C_{max}$ .

Assuming a geometric mean ratio of 0.9 between each pair of formulations and a between subject variability (CV%) of 33%, 93 study participants per group are required to assess BE (using an acceptance range of 0.8 to 1.25) with 80% power at the 5% significance level. In the event that the true mean ratio between each pair of formulations is 0.95, then with the same assumptions on variability and significance level there is >95% power to determine BE for that pair of formulations.

Sample size estimation was performed using SAS software (version 9.4).

Assuming a dropout rate and nonevaluable study participants of approximately 10%, 100 study participants per group for a total of 400 study participants are to be enrolled in the study. If this

10% rate is likely to be exceeded, due to unforeseen circumstances during the COVID-19 pandemic, then participants may be replaced.

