## **2.3 Study design and conduct**

This is a Phase 1, open-label, single-center, randomized, parallel-group, single-dose, 4-arm bioequivalence (BE) study to compare the PK of bimekizumab 320mg when administered as either a 1x2mL or 2x1mL sc injection in healthy male and female study participants. The SS and AI device presentations will be assessed. The 4 arms will be:

[figure not shown]
1. bimekizumab-SS-2mL (test 1)
2. bimekizumab-SS-2x1mL (reference 1)
3. bimekizumab-AI-2mL (test 2)
4. bimekizumab-AI-2x1mL (reference 2)

Two independent comparisons will be made: test 1 versus reference 1 and test 2 versus reference 2.

Four hundred healthy male and female study participants will participate in the study (approximately 100 study participants in each of 4 arms). Each study participant will receive a single-dose administration of bimekizumab 320mg. The duration of the study will be

approximately 168 days, including 27 days of Screening, admission on Day -1, an inhouse Treatment Period from Day 1 to Day 3, Outpatients Visits until Day 112, and a Safety Follow-Up (SFU) Visit on Day 140. Randomization will occur on Day 1 prior to dosing. The schematic diagram of the study is presented in [Figure 2-1](#).

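### SAP 9.2.1 does not say whether the two device pairs share one four-arm ANOVA; if they do, each pair's 90% CI has the wrong width whenever the pairs differ in variability

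*SAP*

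**What the plan says.** SAP 9.2.1 specifies an ANOVA on the ln-transformed AUC, AUC(0-t) and Cmax and adds: "The model will include treatment group as a fixed effect". Protocol 9.4.1 uses the same model wording. Neither section gives the number of levels of the factor or says whether both contrasts come from one fit.

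Some of the text points to one model:
- The model is described in the singular.
- SAP 3.6 lists four treatment groups, and SAP 2.3 plans "approximately 100 study participants in each of 4 arms".
- SAP 9.2.1 says "All participants in the PK-PPS will be included in the analysis as far as the data permit".

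Some of it points to a model per pair:
- "Two independent comparisons will be made" (SAP 9.2.1; similarly in Protocol 9.4.1).
- "The results of the BE analysis will be tabulated, for each comparison", and the CV% is among the tabulated items.

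No other section settles the matter. SAP 9.2.2 reuses the ANOVA for half-life. The SAP 9.2.3 sensitivity analyses follow the primary model and address antibody status, body weight and protein content, not the variance assumption. The interval formula in SAP 9.2.3 gives the t quantile a subscript n and does not define the residual degrees of freedom.

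**The concern.** An ordinary ANOVA over four arms estimates one residual variance. Each Test/Reference contrast uses two arms, but its standard error would be built from all four. If the safety-syringe and auto-injector pairs have different between-subject variability, the pooled value is too small for the noisier pair and too large for the quieter one. The noisier pair's interval is then too narrow and its error at the equivalence limit exceeds 5%. The quieter pair's interval is too wide and it loses some power.

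The plan treats the pairs as separate questions, each with its own bioequivalence conclusion. There is therefore little reason for one pair's interval to depend on the other pair's variability. The two readings also give different intervals from the same data, and that choice should be fixed before concentration data are seen.

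**Working it through.** **Inputs.** Limits 0.80 to 1.25 and 90% CI (SAP 9.2.1). Ratio 0.9, CV 33%, 80% power, 5% level and 93 per group (Protocol 9.9, SAP 2.4). Earlier studies showed CVs of "21% to 25% for AUC and 23% to 33% for" Cmax (Protocol 9.9), not split by device. *Assumptions:* the pair-specific CVs below, equal CVs for test and reference within a pair, and 93 evaluable per arm.

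**1. The plan's own figure.** SD on the ln scale = √ln(1 + 0.33²) = 0.3215. A normal approximation gives n = 2 × 0.3215² × (1.645 + 0.842)² / [ln(0.9/0.8)]² ≈ 92.1, so 93 per group. A full two one-sided tests calculation also gives 93, whether the residual df are 2n − 2 = 184 (power 80.1%) or 4n − 4 = 368 (power 80.2%). At ratio 0.95 power is 97.7%, in line with the stated figure of over 95%. The plan's 93 is reproduced, and it does not reveal which model was intended.

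**2. Interval width under one model.** Pooled SD = √[(SD₁² + SD₂²)/2]. Half-width on the ln scale = t × SD × √(2/93), with t = 1.649 on 368 df (pooled) or 1.653 on 184 df (own pair). For CVs of 33% and 23%:
- The SDs are 0.3215 and 0.2270; the pooled SD is 0.2783.
- Noisier pair: (1.649 × 0.2783) / (1.653 × 0.3215) = 0.863, so the interval is 14% too narrow.
- Quieter pair: (1.649 × 0.2783) / (1.653 × 0.2270) = 1.223, so the interval is 22% too wide.
- The back-transformed half-width factors are 1.0811 (noisier pair, own variance), 1.0566 (quieter pair, own variance) and 1.0696 (pooled). The lowest observed ratio that clears 0.80 is thus 0.80 × 1.0811 = 0.865 for the noisier pair on its own variance, 0.80 × 1.0566 = 0.845 for the quieter pair, and 0.80 × 1.0696 = 0.856 for both under pooling.

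**3. Error at a true ratio of 0.80, for one parameter.** The normal probability of passing was averaged over 4,000,000 simulated draws of the residual variances.

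| Assumed CV, noisier / quieter pair | Pooled model, noisier pair | Pooled model, quieter pair | Separate models, either pair |
|---|---|---|---|
| 33% / 33% | 5.0% | 5.0% | 5.0% |
| 33% / 30% | 5.8% | 4.2% | 5.0% |
| 33% / 28% | 6.3% | 3.7% | 5.0% |
| 25% / 21% (ends of AUC range) | 6.4% | 3.6% | 5.0% |
| 33% / 23% (ends of Cmax range) | 7.7% | 2.2% | 5.0% |

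The worst case is 7.72% by this calculation; simulating 200,000 whole trials gave 7.75%, a difference within simulation error.

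**4. Power at ratio 0.9, CVs 33% and 23%.** The quieter pair has 93.5% pooled against 97.0% separate. The noisier pair has 85.8% pooled against 80.1% separate, but that gain comes only from an interval that is too narrow.

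**5. Cost of separating the models.** At equal CVs the t quantile rises from 1.649 to 1.653 (ratio 1.0025), power is 80.1% against 80.2%, and the required n stays 93.

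**The case against.** The strongest reply is that no wrong choice has been shown. The four-level model is an inference, and the planned independent comparisons with a CV% for each also fit pair-wise models. That stands: a reader might conclude that the plan prescribes pooling, and the text does not go that far.

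Nor is there evidence that the devices differ in variability. Concentration, formulation, dose, route and thigh site are common to all arms (Protocol Table 6-1), and one healthy population is randomised 1:1:1:1 at one centre. The documented CV range lies between small earlier studies, not between devices, so giving one pair the top and the other the bottom is a worst case. This also stands. Protocol 4.2 does describe different injection mechanics for the two devices, which is a reason not to build in equal variance silently, but no proof of a difference.

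The error rates are for one parameter exactly at the limit. Bioequivalence needs AUC, AUC(0-t) and Cmax all to pass, so they bound the decision error from above. The bound is close only if the other two parameters pass almost surely. The power loss is small: 93.5% remains far above 80%. SAP 9.1.1 plans the geometric CV by treatment group, so unequal variability would be visible, although that would not correct the intervals.

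Two further inferences are tempting and fail. One is that the sample size assumed a two-arm variance: the documents apply one CV to each pair, state no degrees of freedom, and 93 results either way. The other is that pooling makes the comparisons not independent. The contrasts use disjoint randomised arms, so their estimates are independent; only the variance estimate would be shared.

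**Conclusion.** The concern holds as an unresolved model specification with a conditional cost. One four-arm ANOVA is the more natural reading of SAP 9.2.1 and Protocol 9.4.1. Under it, each pair's interval is correct only if the two device pairs are equally variable. For the assumed CV gaps, the noisier pair's per-parameter error runs from 5.8% (33/30) to 7.7% (33/23) instead of 5.0%, and the quieter pair's from 4.2% down to 2.2%. With no gap there is no harm. These figures assume 93 evaluable per arm and equal CVs within each pair. A reader might take 7.7% as the trial's expected false-positive rate for bioequivalence. It is not: it combines a worst-case CV split with a single parameter at its limit. The change is worth making because separate models hold 5.0% in every case examined, at almost no cost.

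**What to change.** Before database lock, state in SAP 9.2.1 that each device pair is analysed in its own two-arm ANOVA (SS-2mL versus SS-2x1mL; AI-2mL versus AI-2x1mL), or in one model with a device-specific residual variance. State that the CV% tabulated for each comparison comes from that pair's residual variance. Carry this to the half-life ANOVA in 9.2.2 and the sensitivity analyses in 9.2.3, and define the degrees of freedom in the interval formula there to match. A four-arm pooled model could remain as a sensitivity analysis.

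The cost is a sentence in the SAP and a BY or GROUP statement in the program. Residual df fall from 368 to 184, which widens the interval by about 0.25% if the CVs are equal; the required 93 per group is unchanged. A two-arm ANOVA still assumes equal variance of test and reference within a pair, which matters little with near-equal arm sizes.
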